Participants in Group A will then participate in the NWG intervention. Group A participants will be asked to complete a brief mood scale before and after each walk, and a researcher will complete ethnographic observations during the walk. Follow-up surveys will be completed by those in Groups A and B following the final walking group, and 3 months post-intervention.

Individuals who participated in the NWGs (Group A) will also be invited to a closing reflective focus group at the end of the twelfth walk to discuss their experiences of the groups. Follow-up phone interviews will be conducted with participants from Groups A to find out if they continued walking in nature and any reported longer term impact of the groups. Nature Walking facilitators (Group C) will be invited to participate in a focus group on their experiences delivering in the program.

De-identified aggregated client data to develop a descriptive profile of people using the services will be

provided by each participating site. Group A and B participants will be invited to participate in a member-checking workshop at the conclusion of data analysis. Any changes identified during these workshops will be incorporated into the final findings. Participants will be paid for completing measures as per the schedule listed at Section 10.3.

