7.3 Member-checking workshop

A group workshop will be conducted by investigators to invite Group A, B and C participants to engage with the data analysis process and clarify the findings thus far. Participants who attend will receive a \$50 payment for their time. During this workshop the investigators will engage with the participants in a process called member-checking whereby the participants are invited to provide feedback on the accuracy of the data analysis (McKim, 2023). Specifically, participants will be asked questions along the lines of ‘After hearing about the findings, what are your general thoughts?’; ‘How accurately do you feel the findings captured your thoughts/experiences?’; ‘What could be added to the findings to more accurately capture your experiences?’; ‘Is there anything you would like removed from the data, what would that be and why?’

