9 PROJECT TIMELINES

As shown in Table 5, the project is devised in three phases, 1) establishment, 2) implementation, and 3) analysis and finalisation. The implementation phase of the project will be conducted over eleven months, starting in April 2024 and data collection ceasing in January 2025.

In summary, the establishment phase of the project is as follows; 1) NWG facilitator training, 2) organisational wide readiness survey to be completed by trained NWG facilitators, 3) participant recruitment, project information sessions, screening and obtaining consent from walking and non-walking group participants. The implementation phase consists of 1) the data collection period where quantitative and qualitative is collected (e.g. salivary cortisol-DHEA measures, wellbeing outcome measures (pre- and post- intervention with 3 month follow-up), ethnographic observations, focus groups), and 2) the intervention period, where Group A individuals participate in the NWG. The analysis and finalisation phase comprises 1) the member-checking workshop, 2) data analysis, 3) finalisation of the evaluation and implementation guide, and 4) dissemination activities.

Given variations in weather patterns between the two study sites, the timing of the NWG will vary. Each site will run two separate NWG, each with 10 participants (four groups in total). While there is flexibility in the timing of each group, the timing of data collection will be the same for each group. The timing of the data collection is detailed in Table 6.

Table 5 - Project timelines

		Year/Month																	
		2024												2025					
		Jan	Feb	Mar	Apr	May	Jun	Jul	Aug	Sep	Oct	Nov	Dec	Jan	Feb	Mar	Apr	May	Jun
Establishment	Facilitator training, recruitment planning		x																
	Organisational readiness survey (C)				x														
	Participant recruitment (site information sessions)				x	x	x	x											
Implementation	Data collection period (A&B)				x	x	x	x	x	x	x	x	x						
	NWG intervention period (A)				x	x	x	x	x	x	x								
	Site-wide client data											x							
	Post intervention facilitator focus group (C)												x						
Analysis + finalisation	Member checking workshop (A&B)														x				
	Data analysis (incl. site comparisons)												x	x	x	x			
	Implementation and Evaluation Guide finalised															x			
	On-going dissemination																x	x	x

A = NWG group
 B = non-walking group
 C = NWG facilitators

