Table 6 - Timing of data collection for participants (Group A and B)

	Week																										
Data collection	1	2	3	4	5	6	7	8	9	10	11	12	13	14	15	16	17	18	19	20	21	22	23	24	25	26	27
Pre/post salivary cortisol measure (A&B)**		x											x														
Pre/post & 3 month follow-up survey (A&B)	x												x													x	
NWG intervention (A)^		x	x	x	x	x	x	x	x	x	x	x	x														
Group closing reflective focus group (A)													x														
Post intervention phone interviews (A)															x												

A = NWG group

B = non-walking group

C = NWG facilitators

**Three measures of cortisol; one week prior to the first walk, at the conclusion of the first walk and at the conclusion of the final, twelfth walk

^Ethnographic observations, before and after mood scale

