10 ETHICAL CONSIDERATIONS

10.1 Recruitment and Selection of Participants

Participants will be recruited through the existing caseloads of ICMHS and LikeMind, offering participation to any interested person, capping the number at ten for each NWG. Participants in the research will continue receiving the usual one-on-one support throughout the duration of the research. Participants will be recruited in March-April 2024, with the aim of beginning the NWG sessions at the end of April 2024 and concluding the first group in July 2024. The second group will commence in each site in approximately September, concluding in November. Start and finish dates may vary in each site depending on numbers of participants recruited and weather (too hot or cold). Consumers will be informed about the project by staff of the services. If they express an interest in participating, they will be provided with an information sheet and invited to a NWG information session facilitated by the research team. Consumers who are not interested in participating in the walking groups will also be invited to the study to be part of Group B. Consumers who are interested in participating in Group B will be invited to an information session facilitated by the research team where the study and data collection requirements will be explained, information sheets will be provided and consent to participate sought from volunteers. Potential participants who are unable to attend the information day will have a time organised to meet individually with one of the research team at the study site or via a phone call.

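### On the section 10.1 dates, the second wave's 3-month surveys fall due in or just after the month of the member-checking workshop, and nothing makes the workshop wait for them

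*Protocol*

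**What the plan says.** The protocol touches this in five places.

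- **Section 9, Table 5.** The row "Member checking workshop (A&B" is marked in February 2025. Walks are marked April to October 2024, data collection April to December 2024, and data analysis December 2024 to March 2025. The text of section 9 ends data collection in January 2025.
- **Section 9, Table 6.** Walk 1 is in week 2 and walk 12 in week 13. The row "Pre/post & 3 month follow-up survey (A&B" is marked in weeks 1, 13 and 26. Section 9 says every group keeps this timing.
- **Section 10.1.** "The second group will commence in each site in approximately September, concluding in November". It adds: "Start and finish dates may vary in each site depending on numbers of participants recruited and weather (too hot or cold".
- **Section 7.3.** Participants attend to "engage with the data analysis process and clarify the findings thus far", and a sample question is "After hearing about the findings, what are your general thoughts".
- **Section 3.** It places the "member-checking workshop at the conclusion of data analysis" and says that changes arising from it will go into the final findings.

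Table 1 and Table 4 name the PHQ-ADS as the primary outcome measure. It is part of all three surveys.

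**The concern.** The PHQ-ADS is rated by the participants themselves, who know whether they walked. If someone hears group findings before completing the last survey, those findings can colour the answer, and walkers and non-walkers may be moved differently. The 3-month comparison between Groups A and B would then carry a disclosure effect that cannot be removed afterwards.

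The first wave would not be exposed, because its 3-month surveys come well before any analysis starts. The second wave could be, depending on which of the protocol's dates are followed. No passage makes the workshop conditional on the last survey having been returned.

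**Working it through.** **Inputs.** Table 6: walk 12 is 11 weeks after walk 1 (week 2 to week 13), and the 3-month survey is 13 weeks after walk 12 (week 13 to week 26), so 24 weeks after walk 1. Section 10.1: second groups start about September and end in November 2024. Section 9: four groups of ten, two per site.

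**1. The protocol's own end of data collection.** Counting back from the stated stops:
- Stop on 31 January 2025 (text): latest walk 12 is 31 January minus 13 weeks = 1 November 2024; latest walk 1 is 31 January minus 24 weeks = 16 August 2024.
- Stop on 31 December 2024 (Table 5): latest walk 12 is 1 October 2024; latest walk 1 is 16 July 2024.

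A group starting in September meets neither stop. If walks end in October, as in Table 5 (1 to 31 October), surveys are due 31 December 2024 to 30 January 2025. That fits the January stop and precedes the workshop, but only 1 October fits the December stop.

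**2. Second wave on the section 10.1 dates.**

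| Walk 1 | Walk 12 (+11 weeks) | 3-month survey (+13 weeks) |
|---|---|---|
| 1 September 2024 | 17 November 2024 | 16 February 2025 |
| 14 September 2024 | 30 November 2024 | 1 March 2025 |

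A start on 15 to 30 September would push walk 12 into December and the survey to 2 to 17 March 2025. If only the November finish is used (1 to 30 November), the range is 31 January to 1 March 2025. Twelve weekly walks that begin on or after 1 September cannot end before 17 November, so the October end in Table 5 cannot hold alongside section 10.1.

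**3. First wave.** Walk 1 on 30 April 2024 gives walk 12 on 16 July and the survey on 15 October 2024, before analysis starts in December.

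**4. Who could be exposed.** Second-wave walkers: 2 sites × 1 group × 10 = 20 of 40 (50%). This is a ceiling, since attendance is by invitation and Table 5 gives only a month for the workshop. Group B members surveyed on the same timetable come on top; their number is not given.

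**5. Scale, by assumption only.** The protocol gives no size for a disclosure effect. Suppose hearing findings moved A relative to B by 1 to 2 points throughout the second wave, and that wave is half of each group. The pooled 3-month difference would move by 0.5 to 1 point. Against the planning difference in section 7.1 (22.76 − 16.08 = 6.68) that is 0.5/6.68 = 7% to 1/6.68 = 15%. The planning difference comes from a result immediately after treatment, so this gives only an order of magnitude.

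**The case against.** The strongest reply is that the overlap arises only by joining Table 5's workshop month to section 10.1's walking dates. Read alone, section 9 ends data collection before the workshop, and the section 10.1 dates are approximate. That stands as a description: the firm defect is a contradiction between two timetables. It does not remove the problem, because section 9's dates cannot accommodate a wave that starts in September.

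A reader might infer that participants would be told the PHQ-ADS results. The documents do not say so. Section 7.2 treats member checking as a way to make the qualitative analysis rigorous, and Table 1 lists the workshop with thematic analysis under Aim 3. Against that, section 10.3 says Group B gives only survey data and optional saliva, so any findings about Group B would have to be quantitative. Qualitative findings would also cover perceived effects on mental health (section 7.2). Disclosure is possible but not planned in so many words.

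A reader might also infer that the primary outcome as a whole is compromised for half the walkers. That goes too far. The week-13 rating falls in November on these dates, before analysis begins, and only the 3-month rating is open to influence.

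Finally, one might read section 3 as requiring the workshop to follow all analysis, so that February is wrong in itself. Section 3 also feeds workshop changes into the final findings, so some analysis must come after the workshop.

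**Conclusion.** The point holds as a conflict of dates with a missing safeguard. On the section 10.1 dates and Table 6's interval, second-wave 3-month surveys fall due about 16 February to 1 March 2025, in or just after the workshop month. At most 20 of 40 walkers, plus an unstated number in Group B, could hear findings before their last PHQ-ADS rating.

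This assumes that the second groups start in the first half of September, that the workshop stays in February, and that those invited attend before completing the survey. Whether bias would follow, and how large, cannot be derived from the protocol. It should be fixed because the outcome is unblinded and self-rated, and the safeguard is one sentence.

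**What to change.** 1. Reconcile Table 5, the text of section 9 and section 10.1, so that the second wave's walks, the 3-month surveys and the end of data collection follow one timetable.
2. State in section 7.3 and Table 5 that no group findings are shared with Group A or B participants, and the member-checking workshop is not held, until the last week-26 survey has been returned. On the section 10.1 dates that means not before March 2025.
3. Leave time after the workshop for its feedback to enter the final findings and the guide, as section 3 intends. The workshop need not wait for analysis to close, and findings need not be withheld from facilitators or site co-ordinators on this ground.

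The cost is a delay of about one to two months to the workshop and to the guide, now set for March 2025. This may run into the April to June 2025 dissemination period. No measurement or sample size changes.

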10 ETHICAL CONSIDERATIONS

10.1 Recruitment and Selection of Participants

Participants will be recruited through the existing caseloads of ICMHS and LikeMind, offering participation to any interested person, capping the number at ten for each NWG. Participants in the research will continue receiving the usual one-on-one support throughout the duration of the research. Participants will be recruited in March-April 2024, with the aim of beginning the NWG sessions at the end of April 2024 and concluding the first group in July 2024. The second group will commence in each site in approximately September, concluding in November. Start and finish dates may vary in each site depending on numbers of participants recruited and weather (too hot or cold). Consumers will be informed about the project by staff of the services. If they express an interest in participating, they will be provided with an information sheet and invited to a NWG information session facilitated by the research team. Consumers who are not interested in participating in the walking groups will also be invited to the study to be part of Group B. Consumers who are interested in participating in Group B will be invited to an information session facilitated by the research team where the study and data collection requirements will be explained, information sheets will be provided and consent to participate sought from volunteers. Potential participants who are unable to attend the information day will have a time organised to meet individually with one of the research team at the study site or via a phone call.

10.2 Risk of coercion

The consumers at both sites will receive clinical support regardless of their desire to participate in the research. Therefore, participation in the research is completely voluntary and will not affect their access to mental health support with their usual clinician. This will be made clear in the information sheet and in discussions with interested consumers prior to seeking consent.

10.3 Informed consent

The consent form includes information about the potential benefits of the research, confidentiality, and privacy protections of the study including that the data resulting from participation may be made available to other researchers in the future for secondary data analysis purposes. In these cases, the data will contain no identifying information that could associate participants with it. Participants may consent to participate or not in the study without any consequences. They will be also informed that they can withdraw from the study at any time without repercussions. Participants will be informed that after they sign and return the consent form, it will be retained by the researcher. Participants will be provided with a copy of the Participant Information Sheet (see Appendix 12.3).

The text of the informed consent (see Attachment 12.3 for the full document) includes:

- Participation in this project is voluntary, and consent to be involved in the study can be withdrawn at any time.
- Any consumers not wishing to participate in the walking groups will be offered an option to participate in Group B (non-walking group). These participants would only provide survey data and optional saliva samples.
- Participants may decide not to participate, choose not to answer any question, or stop participating at any time without any penalty.
- They will be informed that if they want to withdraw from the project, they can simply stop participating.
- Participants' real names will not be used at any time.
- There is a small risk of physical injury to participants in the walking group as the research requires participants to be physically active. Specific walking routes (grades 1-3) will be chosen to lessen the likelihood of trips and falls occurring.
- There is no cost or compensation for participation in the walking groups or control groups. However, participants will be reimbursed for their time spent completing measures as per the following:
 - Baseline survey [Groups A and B] \$50
 - Post-intervention survey [Groups A and B] \$50
 - Follow-up survey [Groups A and B] \$50
 - Saliva – 3 samples @ \$20 each [Groups A and B] \$60
 - Post intervention phone interview [Group A] \$40
 - Member-checking workshop [Group A and B] \$50
- Participants will be informed that they can ask questions at any time and will be provided with the contact information of the research team.
- Participant's decision whether to participate in the research study will have no impact on the participants' treatment or involvement with ICMHS or LikeMind, the Rural Health Research Institute, Charles Sturt University or the University of Wollongong.

10.4 Confidentiality and Privacy

All participants in the research study will sign a statement of informed consent. After they sign and return the consent form, it will be retained by the researcher. Participants will be told during recruitment and prior to beginning the study that they can maintain control over the extent, timing and circumstances of what they share during data collection. Participants will also be told that the information shared will be kept confidential, they will not be identified in research results reported, and their information will not be divulged to others in ways that are inconsistent with the understanding of the original disclosure. The information obtained will only be presented in the aggregate.

In reviewing the consent, the researcher will explain any complicated topics, the limits of confidentiality, will make sure that the respondent understands the content of the consent, and will address any questions or concerns that the participants have about the consent and/or about audio-taping prior to obtaining signatures. The researchers will make clear that if the respondent decides that they are uncomfortable with the study as presented in the consent, they can withdraw from the study at any point. The interviews will take place over the phone, so as to ensure convenience and comfort for the participants.

Each participant will be assigned a 2-digit numerical code which will be used to identify the interviews. ICMHS will use codes between 01–50 and LikeMind will use codes between 51–99. All data will be used in aggregate fashion and there will be no mention of participants' real names. Participants will be de-identified in the audio transcripts and in subsequent research dissemination activities such as presentations and publications.

10.5 Safety

There is a potential for participants to become mentally unwell and/or physically unwell during the research. Firstly, the potential for mental health consumers to become acutely mentally unwell is an ever-present issue, however, it is mediated through a complex network of the person's personal coping strategies, their daily routine, social network, and professional medical care. The risk of exacerbation of an acute episode as a direct cause of the research would be considered low, as current research suggests that both physical exertion and experiencing natural environments are stress-relieving rather than inducing. The stress-relieving benefits of engaging with the natural environment have already been discussed and outlined.

As the research requires participants to be physically active, there is a small risk of physical injury. Specific walking routes will be chosen to lessen the likelihood of trips and falls to occur. The NSW National Parks and Wildlife Services offer a grading system for the community to select trails that are suited to their needs, outlined as follows:

- Grade 1 is defined as “No bushwalking experience required. Flat even surface with no steps or steep sections.”
- Grade 2 is described as “No bushwalking experience required. The track is hardened or compacted surface and may have a gentle hill section or sections and occasional steps.”
- Grade 3 is described as “Suitable for most ages and fitness levels. Some bushwalking experience recommended. Tracks may have short steep hill sections, a rough surface and many steps.”
- Grades 4 and 5 require moderate or skilled bushwalking experience.

As a result, all routes chosen in the research will be comprised of Grades 1 to 3.

COVID-19 safety plan will be completed and approved prior to the starting of the group. The plan will depend on the COVID-19 NSW restrictions in place at the time when the group is to be launched. If no groups are allowed to gather, the project will be postponed until the restrictions are lifted.

